15.7 Appendix 7b Burden of Ostomy Care Survey (short survey, after session completion)

BURDEN OF OSTOMY CARE: CHECK-IN REPORT

This study aims to collect information on families' use of ostomy care and supplies, including ostomy-related medications, and ostomy-related health care visits. We ask that you please answer these questions while thinking specifically about your *ostomy-related care*. This is not a test. Please give us your best estimates based on your personal experience.

1. In-person Visits with Wound and Ostomy Care Nurse in the past 4 weeks:

- a. Did you visit a Nurse in person in the past 4 weeks (at a medical office, hospital, and/or in your home)? No (**IF NO**, skip to Question 3. below.) Yes
- b. **IF YES:** How many times did you visit the Nurse in the past 4 weeks? 1 2 3-4
 5-8 More than 8

2. Telephone and/or email consultations with a Wound and Ostomy Care Nurse in the past 4 weeks:

- a. Did you have any telephone and/or web consultations with the Nurse in the past 4 weeks? No (**IF NO**, skip to Question 4. below.) Yes
- b. **IF YES:** How many telephone and/or web consultations have you had with a Wound and Ostomy Care Nurse over the past 4 weeks? 1 2 3-4 5-8 More than 8

3. In-person Visits with a Physician for stoma and/or bowel function problems in the past 4 weeks:

- a. Did you visit a Physician in person for stoma and/or bowel function problems in the past 4 weeks? No (**IF NO**, skip to Question 5. below.) Yes
- b. **IF YES:** How many times did you visit the Physician in the past 4 weeks?
 1 2 3-4 5-8 More than 8

4. What other sources do you use to find more information about your ostomy and daily care? (Fill in all that apply)

- Internet Magazines Other people with an ostomy Support Group
- Other (please specify)

5. If you wear a pouch and have encountered any problems with it, please explain below what those problems are/were?

6. Do you feel comfortable with your daily ostomy care? Yes No
7. On average, how long does it take to do your daily ostomy care?
 0-5 min 5-10 min 10-15 min 15-30 min 30-60min More than 60 min
8. How often do you typically discard a used bag and use a new bag?
 At every emptying Once a day Once every 2-3 days Less often
9. How often do you typically change your wafer on a typical week?
 1 2 3 4-7 More than 7
10. How much time does it usually take you to change your wafer and bag?
 1-15 minutes 16-30 minutes 30-45 minutes 45-60 minutes
 More than 60 minutes
11. Do you usually receive help caring for your stoma and changing your ostomy appliance?
 a. No (skip to Question 12 below)
 b. Yes IF Yes, please check who your helper(s) is(are):
 Spouse/Significant Other Other Family Member Friend Home Care Nurse
 Other Paid Caregiver Other (please specify:) _____

12. Has your bag leaked at any time over the past 4 weeks?
 a. No
 b. Yes IF YES, how many times? 1-4 5-8 More than 8
 i. How many of these times involved a full spillage of your bag contents?
 1-4 5-8 More than 8
 ii. How much time does it usually require to clean up after a bag leak or spill?
 1-30 minutes 31-60 mins. More than 60 mins

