8.2.6 **Survey Follow up.** Telephone contact with respondents will be initiated under four circumstances: 1) for non-respondents (paper survey not returned or RedCap survey not submitted within 2 weeks of mailing or provision of RedCap survey ID); 2) when a returned survey has incomplete or illegible data; 3) when the respondent has questions or requests a call; and 4) if a HADS score is 11 or greater on the depression questions (Appendix 3), the coordinator will inform the participant that this might indicate depression and they should see their physician. This will be documented as a memo in their study file. This will be done within 24 hours of receiving the survey. This will not preclude their participation.

8.2.7 **Returned Survey Processing.** Paper questionnaires returned will be logged in the medical center tracking system. This includes packets returned as "undeliverable, no forwarding address," which would generate a phone call to subject to clarify mailing address. RedCap questionnaires submitted to UA RedCap server will be logged into the Data Core tracking system. Returned paper questionnaires will be stored securely in a locked office or filing cabinet. Each questionnaire will be reviewed for missing responses, improperly marked

responses, handwritten comments on the survey forms, and inserted letters and notes from respondents.

8.2.8 Cleaning PHI. Any comments that reveal PHI will be masked before photocopying paper questionnaires and destroyed in the case of RedCap surveys.

8.2.9 Missing Items. All surveys will be reviewed for completeness based on the criteria outlined below. If the respondent appears to have inadvertently skipped questions, the interviewer will contact the respondent by telephone and attempt to complete the missing items. Unusual situations should be brought to a study project meeting to discuss issues before contacting participant. Use the following guidelines to determine how to handle missing items:

- a. Make all decisions of intent based on marginal notes first (i.e., fill in the answers not bubble filled, but indicated by a written note)
- b. Appropriately skipped questions based on skip patterns will not be counted as missing.
- c. Call backs will be placed when the following criteria are met:
 - i. Full page is missing

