Descriptive statistics will be presented on attendance at training sessions. We will describe and contrast quantity and type of ostomy-care help (professional and lay) sought outside of the training sessions, including calls for support from study Peer Ostomates. Self-reported Peer Ostomate call frequency and duration will be corroborated with a call log maintained by the Peer Ostomate. We will evaluate hypothesized association between OSMT attendance level and outcomes using linear mixed models that have a weighted attendance score as an independent variable. Alternative attendance scores will be tested that give weight to ostomy-care help outside of training sessions.

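### Appendix 7b: the No-skips on questions 1 to 3 each point one question too far, so a respondent who follows the printed interim form bypasses service-use items that apply to them

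*Protocol*

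**What the plan says.** Protocol 8.2.2 assigns the short burden form, Appendix 7b, to the end-of-session survey. Its service-use items look back four weeks. The first three questions each carry a skip for respondents who answer No:

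- Question 1, in-person ostomy nurse visits: "hospital, and/or in your home)? No (IF NO, skip to Question 3. below.) Yes".
- Question 2, headed "2. Telephone and/or email consultations with a Wound and Ostomy Care Nurse in the past 4 weeks": "consultations with the Nurse in the past 4 weeks? No (IF NO, skip to Question 4. below.) Yes".
- Question 3, headed "3. In-person Visits with a Physician for stoma and/or bowel function problems in the past 4 weeks": "bowel function problems in the past 4 weeks? No (IF NO, skip to Question 5. below.) Yes".

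Question 4 asks about other sources of information, including support groups and other people with an ostomy.

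On missing data, Protocol 8.2.9 says: "Appropriately skipped questions based on skip patterns will not be counted as missing". It calls for a telephone callback when a full page is missing or when more than 20% of questions are missing, leaving out open-ended, appropriately skipped and listed sensitive items.

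On use of the data, the SAP (as Protocol 12.2) says: "We will describe and contrast quantity and type of ostomy-care help (professional and lay) sought outside of the training sessions". It also plans alternative attendance scores that give weight to such help.

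**The concern.** A skip after No should pass over only the follow-up parts of the same question. Here each skip also passes over the next whole question. Remote nurse contact would be recorded only for people who also saw a nurse in person. Physician visits would go unrecorded for people who saw a nurse in person but had no remote contact.

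Remote nurse contact is something the protocol itself encourages. Both arms receive ostomy nurse contact information (9.1). Usual-care participants who have never dealt with an ostomy nurse are offered at least a telephone consultation (13.1.1). OSMT participants are reminded that they can contact local nurses (8.1).

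At stake are the interim description and contrast of help sought outside the sessions, and any attendance score that credits such help. Those scores bear on Hypotheses 1.1.3 and 1.2.3. A blank left by a wrong skip looks the same as a legitimate skip. An analyst who reads it as no use would understate use, by an amount that depends on the answer to an earlier question.

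**Working it through.** **Step 1. Where the targets come from.** The two forms side by side:

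| Item | Number in 7a | No-skip in 7a | Number in 7b | No-skip in 7b | Target that fits 7b |
|---|---|---|---|---|---|
| Ostomy type | 1 | none | absent | none | none |
| In-person nurse visits | 2 | 3 | 1 | 3 | 2 |
| Remote nurse consultations | 3 | 4 | 2 | 4 | 3 |
| In-person physician visits | 4 | 5 | 3 | 5 | 4 |
| Other sources | 5 | none | 4 | none | none |

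In 7a each target is the next question. In 7b the items moved down by one and the targets did not. The later skip in 7b, from question 11 to question 12, is right.

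**Step 2. Routing under the printed 7b.** All eight combinations of true answers to questions 1, 2 and 3:

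| Q1 | Q2 | Q3 | Reached, of questions 1 to 5 | Bypassed |
|---|---|---|---|---|
| No | No | No | 1, 3, 5 | 2, 4 |
| No | No | Yes | 1, 3, 4, 5 | 2 |
| No | Yes | No | 1, 3, 5 | 2, 4 |
| No | Yes | Yes | 1, 3, 4, 5 | 2 |
| Yes | No | No | 1, 2, 4, 5 | 3 |
| Yes | No | Yes | 1, 2, 4, 5 | 3 |
| Yes | Yes | No | 1, 2, 3, 5 | 4 |
| Yes | Yes | Yes | 1, 2, 3, 4, 5 | none |

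Question 2 is bypassed in 4 of 8 patterns, question 3 in 2 of 8 and question 4 in 3 of 8. True remote nurse use is lost in 2 of the 4 patterns that have it, and true physician use in 1 of 4. These count logical patterns, not patients. With targets 2, 3 and 4, all eight patterns reach every question.

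**Step 3. Would a callback recover the items?** At most two numbered questions are bypassed. Out of 12, that is 2/12 = 16.7%. Leaving out the open-ended question 5, it is 2/11 = 18.2%. Both are below the trigger of more than 20%, and no full page is missing. Part 2b adds nothing to the count, because it is due only after a Yes to 2a. This counts 7b on its own; a count over the whole survey packet would give a smaller share.

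**Step 4. What happens if blanks are read as none.** The documents give no visit rates, so the following are assumptions for illustration. In-person nurse visits occur in 30% of one arm (A) and 10% of the other (B). True remote use and true physician use are 20% in both arms. The three are independent, and everyone follows the printed form.

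- Never asked question 2: 1 − 0.30 = 70% in A and 1 − 0.10 = 90% in B.
- Recorded remote use: 0.30 × 0.20 = 6% in A and 0.10 × 0.20 = 2% in B.
- Bypassed at question 3: 0.30 × 0.80 = 24% in A and 0.10 × 0.80 = 8% in B.
- Recorded physician use: 0.20 × (1 − 0.24) = 15.2% in A and 0.20 × (1 − 0.08) = 18.4% in B.

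The two spurious differences run in opposite directions. With equal in-person use in the two arms, neither would appear, although both rates would still be too low.

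**The case against.** The strongest reply is that the loss itself is not shown. Protocol 8.2.4 makes RedCap the preferred mode and paper the exception. The RedCap branching is not in the documents and may be right. A paper respondent may also ignore the instruction. This stands: the error is certain in the printed form, and the loss is certain only where that form is followed.

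A reader might infer that the loss differs by arm because the intervention should reduce nurse visits. The documents do not support this. Hypothesis 2.2 expects lower service use in the 6 months after OSMT, whereas 7b covers four weeks at the end of sessions. A difference in that window is possible and no more. A reader might also take the 6% against 2% illustration as a threefold false effect. That ratio is only the assumed 30% against 10% carried through, and it needs blanks to be read as none, which neither document prescribes.

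The affected outcomes are also limited. The Aim 1 scales come from other instruments. The 6-month survey uses 7a, whose nurse and physician skips are right. The SAP's comparison of medical attention names no form or time point, so its dependence on 7b is an inference. Peer calls and OSMT contacts with interventionists are logged separately (9.2.1, 12.8), though those logs cover neither usual care nor clinic visits.

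Finally, 8.2.9 exempts only skips that are appropriate, and a misdirected skip arguably is not. That does not rescue the data, since step 3 already counts the bypassed items as missing and still falls short of the trigger.

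**Conclusion.** The point holds as a routing error in one data-collection form. Three of the skip targets in Appendix 7b are one too high. For printed forms that are followed, everyone without an in-person nurse visit misses the remote nurse item. Those with an in-person visit but no remote contact miss the physician item, and those who answer No on physician visits miss the item on other sources. The callback rule would not bring these back on its own, provided the 20% is counted by question and nothing else is missing.

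The interim data on service use would be selectively incomplete. Treating blanks as no use would bias the contrast of outside help and any attendance score built on it. The size and direction are unknown and vary by item. The documents do not support a claim that most interim data are lost, that the loss is differential by arm, or that Hypothesis 2.2 at 6 months or the primary outcome is compromised. This is a should-fix.

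**What to change.** In Appendix 7b, change the No-skip of question 1 to Question 2, of question 2 to Question 3 and of question 3 to Question 4. Compare the RedCap branching for the interim survey with the corrected form and record the result. For forms already returned, code any item bypassed by a wrong skip as missing, not zero, and report the number of such items by arm and by mode of completion. State this coding rule in the SAP where help outside the sessions and the alternative attendance scores are described.

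In the same pass, correct the skips in Appendix 7a questions 27 to 30, which name their own question number as the target.

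The cost is three changed digits in 7b, a branching check and one sentence in the SAP. The drawback is that some interim values on forms already returned will stay missing.

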9.0 STUDY PLAN

9.1 Usual Care

The UC control program is designed to compare OSMT to usual care to capture the Hawthorne effect. The final intervention for the UC group includes:

- 1) Recommending the patient has met at least once with an ostomy nurse (while likely to have happened in the peri-operative period, it may not be universal);
- 2) Providing the booklet published by The Wound, Ostomy, and Continence Nurses' Society entitled "Basic Ostomy Skin Care: A Guide for Patients and Health Care Providers," with instructions on how to use it;
- 3) Local support group contact information;
- 4) Encouraging patients to have seen their surgeons at least once in follow-up after surgery;
- 5) Contact information for local nutritional and physical therapists; and
- 6) Ostomy nurse contact information. If patients have specific questions about materials, the research coordinator will clarify the content and encourage the patient to call their physician or ostomy nurse about a continuing problem. These resources will also be given to those in the OSMT program.

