9.2.2 Ostomy Care Nurse-Facilitators. We have an experienced OCN-facilitator who will lead sessions from the Tucson site ([name]). She participated in the pilot study and is well-versed in the curriculum. Her back-up in Tucson ([name]) has also been instructed on the curriculum, Ostomy Care Nurse facilitators will train participants to become problem solvers, rather than simply giving them a health professional's solution. They will also participate in weekly research team meetings to give updates on issues and events as they transpire. In this way they will give feedback into what components of the program are problematic, as well as what aspects are working well (program evaluation). There will also be OCNs available at the

University of Pennsylvania (UP), City of Hope (COH) and Yale New Haven (YNH) sites as an added resource for participants.

9.2.3 Specific Ostomy Resource Compendium. We have compiled a Tucson-specific resource compendium to distribute to participants. This includes web-based, OCN resource lists, and personal knowledge to identify local ostomy resources, updated for UP, COH and YNH sites. (Appendix 12)

9.2.4 Program Curriculum. OSMT sessions are described in Table 5 below. The OSMT is organized around several concepts that provide the basis for the content and methods. The CCM points to the need for supporting self-efficacy enhancing, evidence based information and peer support. The CG literature points to the need for CGs to be able to step in and provide assistance when participants are unable to do for themselves, but not to take over totally and create dependency in their family member. The teaching content is divided into five 1.5 - 2 hour sessions: three solely for the participants, one for their CG, and one as a conjoined or single visit. Prior to Session 1, participants will list personal goals for participation in OSMT. Participants will be given an assignment at the completion of Session 2, which will be to monitor ostomy output (frequency and consistency of bowel movements and flatus), and problems related to pouching system. As urinary diversion patients also have interruption of their intestine to make their ostomy, with concomitant obstruction/stomal hernia risks, ostomy output issues may also be applicable to them. This exercise will assist the ostomate in becoming familiar with the relationships between input of food and drink, and ostomy output.

9.2.5 Preparation for sessions.

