13.0 STAKEHOLDER OVERSIGHT

13.1 STAKEHOLDER ROLES

13.1.1 Ostomy Nurses: Ostomy Nurses (WOCNs) will have dual roles in this study: 1) Session leaders, and 2) Research Team participants. Ostomy nurses have actively participated in analysis of the results of the pilot study (Ref 6), as well as the design of the current proposal. In particular, WOCNs have assisted with: 1) identification of cancer survivor and caregiver needs related to ostomy care; 2) addressing nursing deficiencies for ostomates; 3) the curriculum design and plan of delivery; and 4) features of the comparator arm. They will co-lead the sessions and ensure participant and research goals are met. They will participate in weekly calls to report on sessions, help troubleshoot as needed, and ultimately prepare and present findings. The non-Tucson Ostomy Nurses will also be asked to participate in sessions and calls. They may impart suggestions as needed during the calls, and may be asked to lead in future calls. For Usual Care participants, if they have never interacted with an Ostomy Nurse, they will be offered at minimum a telephone consultation.

13.1.2 Peer (buddy) Ostomates: Peer Ostomates are patients who live with ostomies and are well-versed with the curriculum and study objectives. They will have dual roles in the study: 1) Session co-leaders, and 2) Research Team participants. Peers who participated in the pilot will also participate in this study, although peers at other sites, who have been screened and agree to participate, will also be trained in the program and develop rapport with the ostomy nurses who will co-lead sessions. They will also be expected to participate in weekly research calls and impart their thoughts on the sessions and issues that need to be addressed. They will participate in presentation of findings, including at local ostomy group meetings and with major publications.

Peers will be trained over the phone by the PI. The curriculum and the protocol will be reviewed, as well as their roles, and to recommend the participant see their physician for any clinically related issues.

Peers will keep a log of any phone calls they receive, including date, time, length of call, and subject discussed. This will be relayed to site coordinators on a weekly basis.

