**Statistical Analysis Plan**

## Statistical Analysis Plan

**General.** Aim 1 will be analyzed with linear mixed models for repeated measures. Aim 2 will utilize a variety of sources and methods to enumerate the intervention program and ostomy-related family resources in each study arm.

**Aim 1:** Using our enhanced telehealth techniques, determine if **patient activation**, self-efficacy, ostomy-related knowledge, and HRQOL will be improved and sustained over time in the online interactive communication Ostomy Self-Management Telehealth program (OSMT) curriculum compared to a UC group.

Under an intent-to-treat approach, change in outcomes will be evaluated longitudinally with linear mixed models, testing the effect of study arm adjusted for potential confounders. Such models evaluate both associations and rates of change, accounting for within-subject correlation. The Primary Outcome will be PAM. Secondary Outcomes include SE, COH-QOL-CRC scales, and Ostomy Knowledge. Post hoc contrasts will evaluate effect of training (baseline to post) and whether effect is sustained after training (6 month post to follow-up). Standard multivariable modeling procedures will be used to select or eliminate potential confounding variables, starting with candidate variables that are biologically plausible or found to be associated with endpoint change scores (baseline vs. follow-up) in bivariate analyses with a p-value of less than 0.20. Potential candidate covariates and confounders include (but are not limited to) CG participation in training sessions, depression (HADS), time since surgery, ostomy type, age, sex, stage, anticipated permanence of ostomy, and pre- or post-surgical radiation or chemotherapy. We will explore potential interaction for plausible effect modifiers, such as gender, or having a CG.

The COH QOL-CRC assesses ostomy burden and care abilities, including time taken to perform daily ostomy care, comfort with ostomy care, comfort with diet, adjustment of diet for ostomy, appetite, clothing and other problems with ostomy placement. We will also measure clinically related outcomes, including medical attention for problems with bowel, bladder, or ostomy. Changes in these responses will be compared between treatment groups with linear mixed models, chi-square tests or t-tests, as appropriate.

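### The interim burden form does not tell respondents to leave out study contacts, so its remote-nurse item cannot by itself separate OSMT sessions from help obtained elsewhere

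*Protocol*

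**What the plan says.** **The form.** Protocol 8.2.2 places Appendix 7b at the end of sessions, and 9.5 has the surveys go out one day after the last session. Question 2 is headed "Telephone and/or email consultations with a Wound and Ostomy Care Nurse in the past 4 weeks", but the item below it reads "Did you have any telephone and/or web consultations with the Nurse in the past 4 weeks". The heading says email and the item says web. The only guidance on scope is in the introduction, "We ask that you please answer these questions while thinking specifically about your" ostomy-related care. At question 1a, on in-person nurse visits, the direction after No reads "skip to Question 3. below.) Yes" (the last word is the other answer box).

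**The intervention.** Section 9.2.2 states "We have an experienced OCN-facilitator who will lead sessions from the Tucson site", and 9.3 has the sessions run over Zoom.

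**The comparator.** Section 9.1 lists "Recommending the patient has met at least once with an ostomy nurse" and nurse contact details. Section 13.1.1 adds, for usual care (UC), "if they have never interacted with an Ostomy Nurse, they will be offered at minimum a telephone consultation".

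**The planned use.** Protocol 12.2 and the SAP (Aim 1) intend to compare the amount and kind of ostomy help, professional and lay, that participants obtained apart from the sessions. They also intend to try attendance scores that give such help weight. Separately, the SAP says "We will also measure clinically related outcomes, including medical attention for problems with bowel, bladder, or ostomy".

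**The concern.** An OSMT session is ostomy-related, runs over the web and is led by an ostomy nurse. A respondent who has just finished several could fairly report them under question 2. UC has no sessions to report. Any such reporting would make OSMT participants look like heavier users of nurse care at the interim time point, when part of what is measured is the intervention itself.

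Two planned analyses would suffer if they draw on this item: the comparison of help obtained outside the sessions, and the alternative attendance scores, in which a session could be counted once as attendance and again as outside help. Question 2 is the only item on Appendix 7b about remote contact with a nurse.

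**Working it through.** The documents give no figure to reproduce here. The check is date arithmetic plus a reading of the form's routing.

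**1. Sessions in the look-back**

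Inputs from Protocol 8.1, counting from Session 1 as day 0:
- Schedule 1: Sessions 1 and 2 on day 0, Sessions 3 and 4 on day 28.
- Schedule 2: Sessions 1, 2, 3 and 4 on days 0, 7, 21 and 28, with the caregiver session in the gap week.

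If the form is completed L days after Session 4, that is day 28 + L. A session on day s is in the 28-day look-back if (28 + L) − s ≤ 28, that is, if s ≥ L.

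| Completion lag L | Schedule 1 | Schedule 2 | UC |
|---|---|---|---|
| 1 to 7 days | 2 (S3, S4) | 3 (S2, S3, S4) | 0 |
| 8 to 21 days | 2 (S3, S4) | 2 (S3, S4) | 0 |
| 22 to 28 days | 2 (S3, S4) | 1 (S4) | 0 |

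At L = 1, Session 1 is 29 days back and just outside. A form completed on the day of Session 4 (L = 0) would take in all four sessions on either schedule. Section 8.2.6 starts calls to non-respondents after two weeks; at L = 14 both schedules give 2.

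**2. Possible size in OSMT**

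Let f be the share of OSMT respondents who both reach question 2 and report their sessions there, and n the sessions in the window. The mean artefact is f × n. The documents give no value for f, so these are assumed values:

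| f | n = 2 | n = 3 |
|---|---|---|
| 0% | 0 | 0 |
| 10% | 0.2 | 0.3 |
| 25% | 0.5 | 0.75 |
| 50% | 1.0 | 1.5 |
| 100% | 2 | 3 |

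**3. Possible size in UC**

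Let g be the share never seen by an ostomy nurse who accept the offered call, and w the share of those calls inside the four weeks. The mean contribution is g × w × 1. Assuming g of 5% to 20% and w of 0% to 100%, it runs from 0 to 0.20 × 1 × 1 = 0.2.

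**4. Routing on the printed form**

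| Item | No sends the respondent to | Next item in sequence |
|---|---|---|
| 1a (nurse visit in person) | Question 3 | Question 2 |
| 2a (nurse by telephone or web) | Question 4 | Question 3 |
| 3a (physician visit in person) | Question 5 | Question 4 |

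Each skip goes one item too far. The same target numbers are correct in Appendix 7a, where every one of these items carries a number one higher, so they look carried over. If the print is followed, only respondents with an in-person nurse visit reach question 2. That lowers f, but it also drops every genuine remote contact made by someone with no in-person visit.

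**5. Six-month form**

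Follow-up surveys are requested six months after the interim surveys (8.1). The four-week look-back of Appendix 7a then holds no scheduled session, and at baseline sessions have not begun.

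**The case against.** The other side has several good points, and most of them stand.

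- **A reader might infer that the form does count sessions as consultations.** The documents do not show that. They call OSMT contacts sessions or webinars, meaning group teaching for up to six people, and the item asks about consultations under a heading that mentions email. What can be said is that sessions are not excluded.
- **A reader might infer that an OSMT participant who sought no help would report two or three consultations.** On the printed form that person answers No at question 1a and is sent past question 2. The routing of the electronic version is not shown.
- **A reader might infer that the outside-help comparison cannot be made at all.** Attendance is recorded at every session (9.4), staff templates capture telephone and email contacts with interventionists (12.8), and peers log their calls (13.1.2). Part of it can be reconstructed, and the comparison also covers lay and peer help.
- **The UC call is a weak source of contamination.** It is a conditional offer with no date. The Background says usual care typically includes an ostomy nurse during the inpatient stay, so few may qualify. An accepted call is also a real nurse consultation. Sections 9.1 and 13.1.1 are compatible; 9.1 is merely less complete.
- **The SAP's medical-attention sentence is only loosely tied to this item.** It names no form, and question 2 does not ask about problems.

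What survives is narrower. Neither the item nor the form's introduction draws the line that the planned comparison needs, and the existing logs repair this only in part. The skip does not rescue the item, because it removes real contacts along with spurious ones.

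**Conclusion.** The point holds as a fault in one interim item. Two sessions on Schedule 1, and two to three on Schedule 2 at lags of up to 21 days, fall in the look-back of a full attendee, against none in UC. Some OSMT respondents may report them. The resulting bias is anywhere from nothing to two or three consultations per respondent, because the share who would do so is unknown. Unless that share is very small, the error is larger in OSMT than the 0 to 0.2 assumed for UC.

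This rests on three assumptions: sessions run as scheduled without make-ups, the printed routing is not followed by everyone or differs in the electronic form, and question 2 supplies the interim data on remote nurse help, which the plan does not state.

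It would be wrong to carry the point further. PAM is untouched. Hypotheses 2.1 and 2.2 concern the six months after OSMT and are served by Appendix 7a at follow-up, which this route does not reach. The change is worth making because it is cheap and removes an error that differs by arm.

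**What to change.** **Form.** Add to Appendix 7b question 2: *Do not count the study training sessions or any nurse call arranged by the study.* Make the heading and the item name the same modes of contact. Correct the skip numbers at 1a, 2a and 3a, and check that the electronic version matches. Say whether a referral to the site nurse under 9.4 counts as study-arranged, so that the sentence is read alike by everyone. Appendix 7a question 3 can stay as it is; an edit there would gain almost nothing.

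**Comparator.** Log each study-arranged UC nurse call with its date, report these calls as part of the care UC received, and describe the UC package the same way in 9.1 and 13.1.1.

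**Forms already returned.** Flag the form version, run a sensitivity analysis that sets dated session attendance and the contact logs against the answers to question 2, and label the interim between-arm comparison descriptive.

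**Cost.** One sentence, one heading and three skip numbers on one form, one tracked field and a wording reconciliation. The downside is that answers before and after the change are not to identical items, so they should not be pooled without the version flag.
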